- c Includes FVIII activity level (chromogenic substrate FVIII assay and one-stage clotting FVIII assay), Bethesda assay (with Nijmegen modification) for hFVIII inhibitor level, coagulation exploratory assay, and hFVIII protein assay. If a subject has used FVIII within 72 hours of a measurement day, all efforts should be made to obtain FVIII activity measurements when a 72-hour interval without FVIII use is achieved; the 72-hour wash-out period is only intended for subjects who have achieved FVIII ≥ 5 IU/dL at 16 weeks after BMN 270 infusion and who have not resumed FVIII replacement therapy. If FVIII levels are elevated or stable over the course of several weeks, assessment of FVIII activity may be adjusted based on discussion between the Medical Monitor and the Investigator. A D-dimer may be considered under circumstances in which FVIII activity levels are above the normal physiological range and/or if there is a concern for a venous thromboembolism.
- d Blood samples will be collected to evaluate biochemical, molecular, cellular, and genetic/genomic aspects relevant to hemophilia A, coagulation, and/or AAV gene transfer, and to develop assays used for these evaluations. Subjects may choose to opt out of the exploratory genetic/genomic research being done to study or try to discover genes that are not yet known to be associated with hemophilia A. While exploratory samples will be collected at the time points indicated above, testing of these samples (including those for TGA assay and any other exploratory assessments) will be performed only as deemed necessary by the Sponsor.
- ^e Collection for each matrix to occur until at least 3 consecutive results below the limit of detection are obtained.
- f For subjects who have entered 270-301 following participation in 270-902, the scheduled visits at Week 33, Week 34, Week 35, Week 48, Week 46, and Week 50 may be performed by a mobile nursing (MN) professional at the subject's home or another suitable location (if the subject has given written informed consent to participate in MN visits), or at the site as a shortened lab draw-only visit. The MN service or site will collect blood samples at these visits. For site lab draw-only visits, sites will contact the subject via phone call or e-mail to collect information regarding adverse events, changes to concomitant medications, bleeding episodes, and FVIII use. For MN visits, the service will collect this information.

 The physical examination and vital signs assessments listed in the Schedule of Events will not be performed at these MN or lab draw-only visits for subjects who have entered 270-301

^a Complete physical examination should be performed at Week 52; brief physical exam may be performed at other study visits. Weight should be recorded at Week 36 and every 4 weeks through Week 52.

following participation in 270-902. In the event that neither a lab-only visit or MN visit can be conducted within the visit window, the site should telephone the subject to collect adverse event, concomitant medication, and diary data (bleeding events and FVIII usage).

g Subjects who elect to proceed will have a liver biopsy performed during Year 1 post-infusion, at or around Week 52. Additional liver biopsies at times deemed to be clinically relevant (eg decreasing FVIII at a time of increased ALT) may be pursued. Subjects will be asked to consent to the procedure for each liver biopsy performed during the study. Subjects should fast for at least 8 hours prior to liver ultrasound and optional liver biopsies.

Page 55

Table 9.1.5: Schedule of Events – Post-Infusion Follow-Up (Year 2 – Year 5)

	Years 2-5*	Year 2*	Years 3-5*		End of Y	ear Visit		
Assessment				Year 2	Year 3	Year 4	Year 5	ETV
Study Week*	Q12W	Q4W ^g	Q6Wg	W104	W156	W208	W260	
Physical examination ^a	Xa				Х	∠ a		X
Weight ^a	Xa				Х	ζ ^a		X
Assessment of Adverse Events and Concomitant Medications (including review of subject diary for bleeding and FVIII use)	X	X	X		2	X		X
Vital Signs	X				2	X		X
Blood chemistry, hematology, and coagulation tests ^b	X ^b				Х	C b		X
Urine Tests ^b	X ^b				Х	C b		X
Liver Tests ^b	X	X	X	X				X
FVIII assays ^c	X	X	X		2	X		X
AAV5 TAb Assay	X				2	X		X
AAV5 TI Assay	X				2	X		X
FVIII antibody titer	X				2	X		X
Exploratory biomarker assessments ^e	X			X			X	
PBMC Collection (for determination of FVIII and Capsid specific cellular immunity)	X				2	X		X
VWF:Ag	X				2	X		X
TGA Assay ^e	X				2	X		X
PCR of vector DNA in semen ^d	(X) ^d	(X) ^d	(X) ^d		(X	(C) ^d		(X) ^d
PCR of vector DNA in blood, saliva, urine, and stools ^d	(X) ^d				()	(X) ^d		(X) ^d
Haemo-QOL-A assessment	X ^f				Σ	ζ ^f		X
EQ-5D-5L	X ^f				Σ	ζ ^f		X
HAL	X ^f				Σ	ζ ^f		X

	Years 2-5*	Year 2*	Years 3-5*	End of Year Visit				
Assessment				Year 2	Year 3	Year 4	Year 5	ETV
Study Week*	Q12W	Q4W ^g	Q6W ^g	W104	W156	W208	W260	
WPAI+CIQ:HS	Xf			X^{f}				X
PROBE	Xf				Σ	ζ ^f		X
Optional liver biopsy ^h				X				

^{*} Visit windows are ± 2 weeks for visits in Years 2-5. At applicable sites, the Q4W (during Year 2) and Q6W (during Years 3-5) assessments may be conducted by a trained mobile nursing (MN) professional at the subject's home or another suitable location, if the subject has given written informed consent to participate in mobile nursing visits. Q12W and End of Year visits during Years 2-5 cannot be done by a MN professional and must be done at the study site.

^a Complete physical examination should be performed at the End of Year visits; brief physical exam may be performed at other study visits. Weight should be recorded at the second Q12W visit each year and at every End of Year visit during Years 2-5.

b Refer to Table 9.7.8.2.1 for laboratory assessments to be included, and to Table 9.7.8.3.1 for liver tests. LTs may be monitored more or less frequently (and in particular when ALT values are > ULN or ≥ 1.5x baseline value) based on discussion between the Medical Monitor and the Investigator and review of subject data, but LTs will be monitored at least twice weekly during periods when a subject's ALT is ≥ 3x ULN. Subjects with ALT > ULN or ≥ 1.5x baseline value during the study and either an alternative etiology considered or for further evaluation of the lab abnormality may undergo additional evaluations (eg, imaging studies including MRI or ultrasound, additional blood tests, and/or liver biopsy) at the discretion of the Investigator. Additional testing of FVIII and LTs during any study week may be performed if: (1) the ALT has increased to above ULN or increased by > 10 U/L from prior assessment; (2) Increases in ALT values from prior assessment are accompanied by declines in FVIII activity level; or after a discussion between the Medical Monitor and the Investigator based on a review of subject data. If FVIII levels and/or ALT values are stable over the course of several weeks, assessment of FVIII activity and ALT levels may be adjusted based on discussion between the Medical Monitor and the Investigator. During Years 2-5 of the Post-Infusion Follow-Up period, urine tests and blood, chemistry, and coagulation tests should be performed at the second Q12W visit each year and at every End of Year visit.

c Includes FVIII activity level (chromogenic substrate FVIII assay and one-stage clotting FVIII assay), Bethesda assay (with Nijmegen modification) for hFVIII inhibitor level, coagulation exploratory assay, and hFVIII protein assay. If a subject has used FVIII within 72 hours of a measurement day, all efforts should be made to obtain FVIII activity measurements when a 72-hour interval without FVIII use is achieved; the 72-hour wash-out period is only intended for subjects who have achieved FVIII ≥ 5 IU/dL at 16 weeks after BMN 270 infusion and who have not resumed FVIII replacement therapy. If FVIII levels are elevated or stable over the course of several weeks, assessment of FVIII activity may be adjusted based on discussion between the Medical Monitor and the Investigator. A D-dimer may be considered under circumstances in which FVIII activity levels are above the normal physiological range and/or if there is a concern for a venous thromboembolism. If a subject tests positive in the Bethesda assay (with Nijmegen modification) during Years 3-5, a fresh sample should be collected within 4 weeks of the initial visit that had a positive result.

d Sample testing during Long-Term Follow-Up is not required if at least 3 consecutive samples were below the limit of detection during the Post-Infusion Follow-Up period. Subjects who have not had 3 consecutive semen samples below the limit of detection by Week 52 should continue to have PCR testing of semen every 4 weeks (during Year 2) or every 6 weeks (during Years 3-5) until 3 consecutive samples below the limit of detection are documented (or upon consultation between the Investigator and Medical Monitor).

- ^e Blood samples will be collected to evaluate biochemical, molecular, cellular, and genetic/genomic aspects relevant to hemophilia A, coagulation, and/or AAV gene transfer, and to develop assays used for these evaluations. Subjects may choose to opt out of the exploratory genetic/genomic research being done to study or try to discover genes that are not yet known to be associated with hemophilia A. While exploratory samples will be collected at the time points indicated above, testing of these samples (including those for TGA assay and any other exploratory assessments) will be performed only as deemed necessary by the Sponsor.
- f PRO assessments during Years 2-5 of Long-Term Follow-up should be performed at the second Q12W visit each year and at every End of Year visit.
- g Subjects who meet the definition of treatment failure to BMN 270 therapy after Week 52 may omit the Q4W and Q6W visits during Years 2-5, and must attend only the Q12W and End of Year visits. Subjects who are not attending the Q4W/Q6W visits during Years 2-5 may receive a scheduled monthly follow-up telephone call from the site to ask about adverse events, concomitant medications, and bleeding events/FVIII replacement usage. Such subjects following the abbreviated schedule who have not yet cleared vector shedding in one or more matrices must still provide samples in the uncleared matrix Q4W (during Year 2) or Q6W (during Years 3-5) until vector shedding has been cleared, either by reporting to the site to provide samples or by providing those samples to a MN professional.
- h An optional liver biopsy may be performed at any time between Years 2-5 of the study. The optional biopsy may be triggered by a FVIII activity decline by > 50% from steady-state, over 2 consecutive measurements, or by a sustained ALT rise > ULN. If neither triggered is observed, the optional biopsy may be performed at the end of Year 5. Subjects should fast for at least 8 hours prior to liver ultrasound and optional liver biopsies.

Table 9.1.6: Schedule of Events – Therapeutic Corticosteroids for ALT Elevations

			St	eroid Trea	tment Peri		Post-Steroid Period ^c						
	Week 1	Week 2	Week 3	Week 4	Week 5	Week 6	Week 7	Week 8 ^b	Week 1	Week 2	Week 3	Week 4	Week 13
Therapeutic corticosteroids (dose in mg/day) a	60 mg	60 mg	40 mg	40 mg	40 mg	30 mg	20 mg	10 mg					
FVIII activity testing									X	X	X	X	
Liver tests									X	X	X	X	
Hepatitis B testing ^d						X			X				X
HCV Viral Loadd						X			X				X

^a Therapeutic oral corticosteroids may be initiated according to the parameters set out in Section 9.4.8.2.

b Following initiation or completion of steroid regimen, if a recurrence of ALT values > ULN or ≥ 1.5x baseline value is reported, steroid management decisions will based on discussions between the Investigator and Medical Monitor. Modification of the steroid regimen may take into consideration possible confounders for the ALT elevation, relationship between increases in ALT and FVIII activity, ALT/FVIII levels post steroid initiation, and adverse events related to steroid dosing. Guidance for tapering oral corticosteroid dosing can be found in Section 9.4.8.2.

^c After discontinuation of oral corticosteroids, weekly labs for ALT and FVIII levels will be measured once a week for 4 weeks to ensure stability in values. If these assessments are already being done as part of normal study follow-up, they do not need to be duplicated.

^d Should only be performed in subjects with a history of hepatitis B or hepatitis C prior to study entry.

Table 9.1.7: Schedule of Events – Optional Liver Biopsy

	Within 28 Days Before Biopsy Day	Within 7 Days Before Biopsy Day	Biopsy Day (BD)
Informed Consent for Liver Biopsy Procedure	X		
Liver Ultrasound ^a	X		
Physical examination	X		X
Hematology, Coagulation, Chemistry Assessments ^b	X		X
Liver Tests ^b	X		X
FibroScan	X		
FVIII Activity Level Assessment (central and local)		X	X*
Exploratory CK18 and Grp78 assessment		X	X^*
Pre-Biopsy Consultation ^c		X	
Liver Biopsy ^d			X
PBMC Collection (whole blood draw)			Xe

If Day -28 assessments are already performed as part of a scheduled on-site study visit, they do not need to be duplicated here.

^{*} If the Day -7 and biopsy day visits occur on the same day, these tests do not need to be duplicated.

^a Liver ultrasound must be performed within 28 days prior to the scheduled biopsy. Subjects should fast for at least 8 hours prior to liver ultrasound.

^b Refer to Table 9.7.8.2.1 for laboratory assessments to be included, and to Table 9.7.8.3.1 for liver tests.

^c Subjects will undergo a pre-biopsy consultation with the Investigator (treating hematologist) and hepatologist and/or radiologist.

d Subjects should fast for at least 8 hours prior to optional liver biopsy. Biopsy will be a percutaneous or transjugular biopsy under ultrasound guidance, performed according to the standard procedure of the institution. If only a small amount of tissue (< 2 cm) is obtained at the time of the biopsy, the subject may be asked to consent for a second pass. In this case, the original < 2 cm sample should still be retained and handled according to the instructions for handling biopsy specimens in the Laboratory Manual. Following completion of the biopsy, the subject should remain in the hospital under observation for at least 4-6 hours. Overnight post-procedure observation may be done at the investigator's discretion.

^e Blood draw for PBMC collection should be performed on the biopsy day or ± 1 week from the biopsy day.

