Change of the hFVIII activity, as measured by chromogenic substrate assay, during
Weeks 49-52 post-BMN 270 infusion from baseline. Each subject's hFVIII activity during
Weeks 49-52 is defined as the median of the values obtained during this 4-week window.
Values for hFVIII activity will be excluded if obtained within 72 hours since the last
infusion of exogenous FVIII protein concentrates.

Secondary efficacy endpoints:

- Change in the annualized utilization (IU/kg) of exogenous FVIII replacement therapy during Week 5 to Week 52 post-BMN 270 infusion from the baseline utilization of exogenous FVIII replacement therapy.
- Change in the annualized number of bleeding episodes requiring exogenous FVIII replacement treatment (annualized bleeding rate, ABR) during Week 5 to Week 52 of the study post-BMN 270 infusion from the baseline ABR.

NAME OF COMPANY	SUMMARY TABLE	FOR NATIONAL
BioMarin Pharmaceutical Inc.	Referring to Part of the	AUTHORITY USE
[name]	Dossier:	ONLY:
[name]		
	Volume:	
NAME OF FINISHED PRODUCT:		
BMN 270	Page:	
NAME OF ACTIVE DICHEDIENT		
NAME OF ACTIVE INGREDIENT:	Reference:	
AAV5-hFVIII-SQ		

Tertiary efficacy endpoints:

- Change from baseline in the total score of HAEMO-QoL-A at Week 52 of the study post-BMN 270 infusion.
- Change from baseline in the EQ-5D-5L score at Week 52 of the study post-BMN 270 infusion.
- Change from baseline in the Haemophilia Activities List (HAL) score at Week 52 of the study post-BMN 270 infusion.
- Change from baseline in the Work Productivity and Activity Impairment plus Classroom Impairment Questions: Hemophilia Specific (WPAI+CIQ:HS) score at Week 52 of the study post-BMN 270 infusion.
- Change from baseline in Patient Reported Outcomes, Burdens, and Experiences (PROBE) score at Week 52 of the study post-BMN 270 infusion.

Safety:

The following safety outcome measurements will be assessed:

- Incidence of adverse events (AEs) and serious AEs (SAEs)
- Change in clinical laboratory tests (serum chemistry and hematology)
- Change in vital signs
- Change in physical examination
- Vector shedding (blood, urine, semen, stool, saliva)
- Liver tests (LTs, including ALT, AST, GGT, direct and total bilirubin, lactate dehydrogenase][LDH], and alkaline phosphatase)
- Immune response to FVIII transgene product and AAV5 capsid proteins

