An analytic sample size of 110 will also have at least 95% power to demonstrate that the change in the annualized number of bleeding episodes requiring exogenous FVIII replacement treatment (ABR) during Week 5 to Week 52 of the study post-BMN 270 infusion from the baseline ABR is less than 3.5 (non-inferiority margin), assuming the pre- and post-BMN 270 infusion population mean ABRs are 3.5 and 1 respectively, using a one-sample t-test with a 2-sided significance level of 0.05. Under the same assumptions, a sample size of 110 will have approximately 90% power to demonstrate that the change is less than 0, i.e. superiority of BMN 270 against FVIII prophylaxis.

Overall, the planned sample size will have greater than 80% power for testing the primary and secondary efficacy endpoints hierarchically with a 2-sided significance level of 0.05.

Analysis Population

The intention-to-treat (ITT) population is defined as all subjects who receive BMN 270 infusion, and the modified intention-to-treat (mITT) population is defined as subjects who receive BMN 270 infusion and are HIV-negative. The mITT population will be used for the primary efficacy

NAME OF COMPANY	SUMMARY TABLE	FOR NATIONAL
BioMarin Pharmaceutical Inc.	Referring to Part of the	AUTHORITY USE
[name]	Dossier:	ONLY:
[name]		
	Volume:	
NAME OF FINISHED PRODUCT:		
BMN 270	Page:	
NAME OF ACTIVE INCREDIENT.		
NAME OF ACTIVE INGREDIENT:	Reference:	
AAV5-hFVIII-SQ		

analysis, and the ITT population will be used for the supportive efficacy analysis. The ITT population will also be used for the safety analysis.

Analysis

For the primary efficacy endpoint at Week 52 (ie, the change in the hFVIII activity during Weeks 49-52 post-BMN 270 infusion from baseline, as measured by chromogenic substrate assay), a one-sample t-test will be used to test the null hypothesis that the change is 0 or less against the alternative hypothesis that the change is greater than 0. Descriptive summaries of the proportions of subjects whose FVIII activity during Weeks 49-52 is greater than or equal to select thresholds, such as 15, 25 and 30 IU/dL, and the confidence intervals of the proportions will also be provided.

For the secondary endpoints, the analyses will be performed on 110 subjects in the mITT population whose baseline data will be prospectively collected for approximately 6 months in the non-interventional study 270-902 prior to their enrollment in 270-301.

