For the first secondary efficacy endpoint at Week 52 (ie, the change in the annualized utilization (IU/kg) of exogenous FVIII replacement therapy during Weeks 5-52 post-BMN 270 infusion from baseline), a one-sample t-test will be performed to test the null hypothesis that the change is 0 or greater against the alternative hypothesis that the change is less than 0.

For the second secondary efficacy endpoint at Week 52 (ie, the change in the annualized number of bleeding episodes requiring exogenous FVIII replacement treatment during Weeks 5-52 post-BMN 270 infusion from baseline), a one-sample t-test will be performed to test for non-inferiority of BMN 270 against FVIII prophylaxis (ie, the baseline ABR calculated using subjects' data collected in 270-902) using a margin of 3.5, ie, to test the null hypothesis that the change is 3.5 or greater against the alternative hypothesis that the change is less than 3.5. If non-inferiority is demonstrated, the test for superiority of BMN 270 against FVIII prophylaxis will be performed.

The primary efficacy endpoint and secondary efficacy endpoints will be tested hierarchically according to the order described above.

Two interim analyses were planned, after approximately 16 and 20 treated HIV-negative subjects, respectively, completed the Week 26 visit (or have discontinued study participation prior to Week 26). The first interim analysis was performed as planned in May 2019. Based on the interim results and the totality of the data, the secondary interim analysis was deemed unnecessary. The DMC reviewed the interim analysis results to assess the efficacy and safety profiles, whether the pre-specified criteria of statistical significance has been achieved, and the risk/benefit ratio of the interventions in the BMN 270 studies based on the totality of the data. The primary efficacy endpoint for the interim analyses involves hFVIII activity, as measured by chromogenic substrate assay, achieved post-BMN 270 infusion, as detailed in the statistical analysis plan (SAP).

NAME OF COMPANY	SUMMARY TABLE	FOR NATIONAL
BioMarin Pharmaceutical Inc.	Referring to Part of the	AUTHORITY USE
[name]	Dossier:	ONLY:
[name]		
	Volume:	
NAME OF FINISHED PRODUCT:		
3MN 270	Page:	
NAME OF ACTIVE INCIDENT		
NAME OF ACTIVE INGREDIENT:	Reference:	
AAV5-hFVIII-SQ		

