Two interim analyses were planned, after the first approximately 16 and 20 treated HIV-negative subjects, respectively, completed the Week 26 visit (or have discontinued study participation prior to Week 26). The first interim analysis was performed as planned in May 2019. Based on the interim results and the totality of the data, the secondary interim analysis was deemed unnecessary. The DMC reviewed interim analysis results to assess the efficacy and safety profiles, whether the pre-specified criteria of statistical significance has been achieved, and the risk/benefit ratio of the interventions in the BMN 270 studies based on the totality of the data.

The final analysis for the study will be performed after all subjects have been followed for 52 weeks post-BMN 270 infusion. After the final analysis, safety and efficacy will then continue to be assessed long-term in all subjects for a total of approximately 5 years.

To avoid breakthrough bleeding, subjects will only discontinue exogenous prophylactic FVIII replacement therapy after 4 weeks following infusion of BMN 270. Four weeks represents the time by which endogenous production of FVIII following gene transfer is expected to be efficacious, based on earlier results.

As the relationship between activity assay results of the BMN 270 gene product and bleeding remains to be established, Investigators should strive to minimize bias by avoiding consideration of FVIII activity levels by themselves or subjects in the reporting of bleeding episodes and FVIII usage.

In subjects who experience recurrent bleeding episodes, the Investigator and Medical Monitor will discuss whether to resume prior FVIII prophylaxis.

Subjects who do not respond to BMN 270 treatment (ie, treatment failure, manifesting as either failure to achieve FVIII activity ≥ 5 IU/dL by Week 52 or inability to maintain independence from prophylactic FVIII replacement therapy due to joint bleeding episodes, in the judgment of the Investigator) may, at the Investigator's discretion and after discussion with the Medical Monitor or Sponsor-designated Data Monitor, follow an abbreviated visit schedule after Week 52 of the study by attending only the Q12W and End of Year visits during Years 2-5. Subjects who are not attending the Q4W/Q6W visits during Years 2-5 may receive a scheduled monthly follow-up telephone call from the site to ask about adverse events, concomitant medications, and bleeding events/FVIII replacement usage.

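### The bleeding rate counts all of Weeks 5-52, including time after prophylaxis is resumed for recurrent bleeding, which dilutes failures in a non-inferiority test against that same prophylaxis

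*Protocol*

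**What the plan says.** The Synopsis of Amendment 6 defines the second secondary endpoint as "Change in the annualized number of bleeding episodes requiring exogenous FVIII replacement treatment (annualized bleeding rate, ABR) during Week 5 to Week 52", compared with baseline. Section 9.7.3.1 uses the same window. Neither place attaches a condition to it.

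The test is "non-inferiority of BMN 270 against FVIII prophylaxis (ie, the baseline ABR calculated using subjects' data collected in 270-902) using a margin of 3.5", that is, "to test the null hypothesis that the change is 3.5 or greater against the alternative hypothesis that the change is less than 3.5". Superiority follows if non-inferiority is shown.

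Regular prophylaxis stops 4 weeks after infusion. Section 9.1, repeated in substance in the Synopsis and Section 9.7.3.1, then states: "In subjects who experience recurrent bleeding episodes, the Investigator and Medical Monitor will discuss whether to resume prior FVIII prophylaxis". Section 9.1 counts "inability to maintain independence from prophylactic FVIII replacement therapy due to joint bleeding episodes" as treatment failure, but the only consequence it gives is a lighter visit schedule after Week 52. Section 9.4.8.1 separately allows prophylactic FVIII case by case, for example around surgery.

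The protocol does deal with exogenous FVIII for the primary endpoint: activity values within 72 hours of an infusion are excluded. For ABR, Section 14.3 (shown in Amendment 4) imputes a missing change by the median of the observed changes. It adds a negative binomial model, an observed-case analysis and possible multiple imputation as sensitivity analyses. None of these concerns resumed prophylaxis.

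**The concern.** The rescue is the comparator, and the endpoint event itself triggers it. A subject who bleeds repeatedly and returns to his earlier regimen is expected, from then on, to bleed at about his baseline rate. Because the window is fixed and unqualified, that time enters the post-infusion ABR as if BMN 270 had produced it. In a superiority test against an inferior control this would be a familiar treatment-policy choice. In a non-inferiority test against prophylaxis, time spent on prophylaxis has an expected change near 0, well inside a margin of +3.5, so it moves the mean toward a pass.

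At stake is what a positive result means. As written, it would show that BMN 270 with return to prophylaxis as needed is not much worse than prophylaxis. The protocol describes the test as one of BMN 270 against prophylaxis.

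**Working it through.** **Inputs from the protocol.** n = 110; mean ABR 3.5 before and 1 after infusion (change -2.5); SDs 7.8 and 1.8 with zero correlation; margin 3.5; one-sample t-test at two-sided 0.05 (Synopsis; Section 14.7 of Amendment 4). On-demand ABR in the study rationale: 4.5-18 in a retrospective study and 20-60 in prospective studies.

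**Assumptions not in the protocol.** The share f who resume, the weeks w of the 48 before they do, and each such subject's off-prophylaxis ABR R, taken from the on-demand ranges. After resumption ABR returns to 3.5. All others change by -2.5.

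**1. The plan's own figures.** SD of change = sqrt(7.8² + 1.8²) = 8.0. The noncentral t gives superiority power of 90.1% (stated: about 90%) and non-inferiority power above 99.9% (stated: at least 95%). Both reproduce.

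**2. Where the test passes.** SE = 8/sqrt(110) = 0.763. With a critical t of about 1.98, non-inferiority is declared at any observed mean change up to 3.5 - 1.98 × 0.763 = about +1.99.

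**3. Limiting case.** Everyone is back on prophylaxis from Week 5 with mean change 0. Power for non-inferiority is 99.5% at SD 8. If both periods have the prophylaxis SD and are uncorrelated, SD = 7.8 × sqrt(2) = 11.0 and power is 91%.

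**4. One subject who resumes.** Counted change = [wR + (48 - w) × 3.5]/48 - 3.5. Off-prophylaxis change = R - 3.5.
- R = 18, w = 24: +7.25 counted, +14.5 off prophylaxis.
- R = 18, w = 12: (216 + 126)/48 - 3.5 = +3.6 counted, +14.5 off prophylaxis.

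**5. Group mean** = f × (his change) + (1 - f) × (-2.5). Power is for non-inferiority at SD 8.

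| f | R | w | Mean as counted (power) | Mean off prophylaxis (power) |
|---|---|---|---|---|
| 5% | 18 | 24 | -2.0 (about 100%) | -1.65 (about 100%) |
| 10% | 20 | 24 | -1.4 (about 100%) | -0.6 (about 100%) |
| 30% | 4.5 | 12 | -1.68 (about 100%) | -1.45 (about 100%) |
| 20% | 18 | 12 | -1.27 (about 100%) | +0.9 (92%) |
| 30% | 18 | 12 | -0.66 (about 100%) | +2.6 (21.5%) |
| 40% | 18 | 12 | -0.05 (99.6%) | +4.3 (0.1%) |

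At R = 18 and w = 12 the mean reaches the margin when f = 6/(change + 2.5). Off prophylaxis that is 6/17 = 35%. As counted it is 6/6.125 = 98%.

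**6. Check on the SD.** A mixture widens the SD by f(1 - f) × (his change + 2.5)². In the last row this gives sqrt(64 + 9.0) = 8.5 as counted and sqrt(64 + 69.4) = 11.5 off prophylaxis. Power becomes 99.1% and 0.4%, so the contrast remains.

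**The case against.** A reader might infer that failures count toward non-inferiority. They do not. Every treated bleed from Week 5 to resumption is counted, and in step 4 the subject who resumes scores +7.25 or +3.6, both above the margin. He counts against BMN 270, only less than he would off prophylaxis.

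A reader might also infer that the worse the failure, the less he counts. At fixed timing the reverse holds: at R = 60 and w = 24 the counted change is (60 + 3.5)/2 - 3.5 = +28.25. With 10% such subjects the mean is +0.58, the SD rises to about 12 and non-inferiority power as counted falls to roughly 70%. The inference would need resumption to come sooner as bleeding worsens, and the protocol sets no such timing.

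Three further objections have weight.
- Counting all treated bleeds over a fixed window is a recognised treatment-policy strategy. That stands, but it answers a different question from the comparison the protocol names.
- FVIII utilization is tested before ABR and registers resumed prophylaxis as use. That makes resumption visible, but the test needs only a mean reduction below 0 and does not correct the ABR.
- The SAP and Section 14 of Amendment 6 are not at hand and could contain a rule. However, the Amendment 6 summary says its changes leave the endpoint definition and the final efficacy methods as they were. The protocol itself already fixes the window, hypotheses, test, missing-data rule and sensitivity analyses. Resumed time is observed, so the missing-data rule does not reach it.

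Resumption is also a matter for discussion and not automatic, and no document figure says how many subjects would resume.

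**Conclusion.** The point stands as one of dilution. Followed as written, the plan scores post-resumption time under the comparator and biases the ABR difference toward a non-inferiority pass. The direction follows from the protocol's own definitions. The size does not: it depends on how many resume, how early, and how they would have bled otherwise. It is negligible at an off-prophylaxis ABR of 4.5, and with 5% (ABR 18) or 10% (ABR 20) resuming mid-period non-inferiority passes either way. It can reverse the conclusion if many resume early, as with 40% at an ABR of 18 after 12 weeks. The on-demand ranges come from patients without gene transfer and may overstate R in a partial responder. The documents do not support saying that the trial's ABR result will be wrong. They support saying that the as-observed ABR alone cannot exclude this problem.

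**What to change.** Leave every clinical rule as it is and change only the analysis.

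1. Define resumption of prophylaxis for bleeding as an intercurrent event for ABR, and distinguish it by recorded reason from short-term use such as peri-operative cover.
2. Prespecify an ABR analysis that does not credit post-resumption time to BMN 270. One option assigns that time a stated, unfavourable off-prophylaxis rate. Another uses ABR on time off prophylaxis and takes the reason for resumption into account. Do not simply carry forward the subject's own rate up to resumption: a run of bleeds triggers resumption, so that rate is biased upward.
3. Report this beside the as-observed Week 5-52 ABR, with the number who resume and when.
4. If the two disagree, do not claim non-inferiority to prophylaxis from the as-observed ABR alone.

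The cost is wording and a little more analysis. FVIII use and bleeds are already in the diary (Section 9.7.3.1), and the eCRF infusion pages carry a category for use (Section 9.7.7.1). The downside is a somewhat less favourable ABR. Enrolment is complete and an interim analysis has been done, so the rule should be fixed and dated before the final analysis by people without access to the bleeding data, in line with the data access plan in Section 9.4.7.
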